At dose escalation levels 2 and 3 and in the phase II portion each patient will receive a test dose of 3×10^6 IU for their first injection prior to escalation to higher doses according to our published guidelines. For example, at dose level 3 each patient will receive an initial test dose of 3×10^6 IU of IL-2, which will be escalated to 7×10^6 for the second treatment and then 15×10^6 IU for the final two treatments as tolerated. If a dose level is not tolerated the treatment will be de-escalated to previous dose levels for subsequent treatments. If 3 million IU IL-2 is not tolerated the dose can be de-escalated to 1 million IU IL-2. If 1 million IU IL-2 is not tolerated the treatment will be deemed intolerable and patient removed from study (see Figure 6).

Patients will be assessed by a physician once during the first week of radiotherapy, weekly during intralesional IL-2 injections, and with every cycle of pembrolizumab. Routine laboratory evaluation will occur pre-treatment. For response assessment patient will have imaging pre-treatment and after every three cycles of Pembrolizumab. For collateral studies patients will undergo mandatory treatment lesion biopsies and blood draws pre-treatment and during the needle placement for the final IL-2 treatment.

Preliminary efficacy as determined by abscopal response rate, ORR, DCR and PFS will be assessed every 3 cycles. Patients on active treatment at 12 months may continue to receive pembrolizumab but will revert to standard of care (SOC) management and be labeled in “follow up”. At this time only PFS and long-term toxicity data will be collected every 3 months.

The primary endpoint is to determine if this regimen converts patients with resistance to PD-1/PD-L1 checkpoint blockade into responders as determined by abscopal response rate (defined as response rate at lesions not treated with RT + IL-2) using irRECIST as well as ORR, DCR, and PFS using RECIST 1.1. The secondary endpoint is tolerability, safety, and toxicity using CTCAE v4.03. Correlative studies include immunophenotyping serial tumor biopsies and blood samples.

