5.2.2.3 Interleukin-2

Interleukin-2 will be delivered into the treatment lesion by intralesional injections starting 24-96 hours after the completion of radiotherapy and to be completed during Cycle 2. Once needle is placed, intralesional IL-2 will be administered by qualified personnel. Intralesional IL-2 injections will follow guidelines, which we have previously published [46]. Briefly, each patient will receive an initial dose of 3×10^6 IU of IL-2, which will be escalated to 7×10^6 for the second treatment and then 15×10^6 IU for the final two treatments as tolerated. At dose escalation levels 2 and 3, each patient will receive a test of 3×10^6 IU for their first injection prior to escalation to higher doses according to our published guidelines. If a dose level is not tolerated (i.e., grade 3-4 non-hematologic toxicity) the treatment will be de-escalated to previous dose levels for subsequent treatments. If the initial dose of 3×10^6 IU of IL-2 is not tolerated the dose can be reduced to 1 million IU. Safety and toxicity will be evaluated using CTCAE v4.03. A dose limiting toxicity (DLT) will be defined as a treatment related grade 3-4 toxicity non-hematologic toxicity and will require dose de-escalation. If a DLT does not resolve within 5 days, is not responsive to management, or occurs at the lowest dose level (1 million IU IL-2) after de-escalation then that patient will be removed from trial and the therapy will be deemed intolerable. Therapy will be deemed safe and tolerable if no greater than 33% of patients find the treatment intolerable.

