Phase II will be conducted using the MTD. For phase II, a treatment limiting toxicity (TLT) will be defined as an IL-2 treatment related grade 3-4 non-hematologic or grade 4 hematologic toxicity and will require dose de-escalation. A TLT must resolve to grade 2 or less before the next de-escalated dose is administered. Treatment intolerance will be measured in phase II to define the percentage of patients that have to come off study treatment or miss an IL-2 treatment due to inability to tolerate the full course of therapy. This is a separate measure from the MTD assessment in phase I and is only measured during phase II. Treatment intolerance will be defined as a TLT that does not resolve to grade 2 or less within 5 days, is not responsive to management, or occurs at the lowest dose level (1 million IU IL-2). In this case the patient will be removed from trial and the therapy will be deemed intolerable for that patient. If a dose of IL-2 is missed due to TLT not resolving to grade 2 or less within 5 days this falls into the definition of treatment intolerance. If a dose IL-2 is missed for other reasons this does not qualify as treatment intolerance. The TLT period begins with the administration of IL-2 and lasts up to 7 days after the last injection of IL-2. As outlined above the initial dose of intralesional IL-2 will be administered as 3 million IU test dose. If there are IL-2 related grade 3-4 non-hematologic or grade 4 hematologic treatment related adverse effects the dose will be de-escalated for the second treatment to 1 million IU. If there are grade 3-4 non-hematologic adverse effects, or grade 4 hematologic adverse effects at the 1 million IU dose the patient will be removed from study and the therapy deemed intolerable. For a given patient dose escalation will occur if there are no IL-2 related grade 3-4 non-hematologic or grade 4 hematologic treatment related toxicities. For each patient if a dose level is associated with grade 3-4 non-hematologic or grade 4 hematologic toxicity this will be deemed a TLT and the patient will be de-escalated to the lower dose for the next treatment. Once the dose is decreased there will be no further dose re-escalation allowed for an individual patient. If a planned dose cannot be delivered within the prescribed week it will be skipped.

Intratumoral IL-2 is well tolerated per Table 1 above with the majority of patients experiencing mild toxicity.

Table 7. Adverse Event Management

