- g. CT or MRI at pre-treatment and q 3 cycles until progression (e.g., at the end of cycle 3, ,6, 9, etc.).
- h. See the correlative study section for detailed information (Section 8.0)
- i. Biopsy: Tumor biopsies will be obtained prior to cycle 1 treatment and during the final intralesional needle placement for IL-2 delivery (Cycle 2 Week 3).
- j. Follow-up: patients on active treatment at 12 months may continue to receive pembrolizumab, but will revert to SOC management and be labeled in "follow-up". At this time only PFS and long-term toxicity data will be collected every 3 months as part of routine SOC management.
- k. Research blood to be drawn prior to starting therapy for cycle 1 and 2. After Cycle 3 research blood to be drawn at cycle 6 then every 6 cycles thereafter.
- l. Stool sample will be collected from patients before initiation of treatment

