ARR is defined as the percentage of patients that achieve an objective tumor response at unirradiated lesions as defined by irRECIST criteria.

Reporting of Results

All patients included in the study must be assessed for response to treatment, even if there are major protocol treatment deviations or if they are ineligible. Each patient will be assigned one of the following categories: 1) complete response, 2) partial response, 3) stable disease, 4) progressive disease, 5) early death from malignant disease, 6) early death from toxicity, 7) early death because of other cause, or 9) unknown (not assessable, insufficient data).

All of the patients who met the eligibility criteria should be included in the main analysis of the response rate. Patients in response categories 4-9 should be considered as failing to respond to treatment (disease progression). Thus, an incorrect treatment schedule or drug administration does not result in exclusion from the analysis of the response rate. Precise definitions for categories 4-9 will be protocol specific.

All conclusions should be based on all eligible patients. Subanalyses may then be performed on the basis of a subset of patients, excluding those for whom major protocol deviations have been identified (e.g., early death due to other reasons, early discontinuation of treatment, major protocol violations, etc.). However, these subanalyses may not serve as the basis for drawing conclusions concerning treatment efficacy, and the reasons for excluding patients from the analysis should be clearly reported.

The 95% confidence intervals should be provided.

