9.3 Safety

The adverse events observed will be summarized as frequency, proportion of patients, and exact 95% confidence interval for proportion, categorized by type (organ affected or laboratory determination), severity by CTCAE v4.03 and nadir or maximum values for the laboratory measures), time of onset (i.e., course number), duration, and reversibility or outcome. Tables will be created to summarize these toxicities by dose and course. The secondary endpoint is safety and toxicity. A treatment limiting toxicity (TLT) will be defined as a treatment related grade 3-4 non-hematologic toxicity and will require dose de-escalation. If a TLT does not resolve within 5 days, is not responsive to management, or occurs at the lowest dose level (1 million IU IL-2) after de-escalation then that patient will be removed from trial and the therapy will be deemed intolerable. Therapy will be deemed safe and tolerable if no greater than 33% of patients find the treatment intolerable.

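### Patients who cannot tolerate IL-2 are to be removed from the trial, usually before the first response scan, and the follow-up sections do not clearly keep their primary-endpoint assessments

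*Combined protocol and SAP*

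**What the plan says.** **Removal.** Section 5.4.1.2 defines treatment intolerance as a treatment limiting toxicity (TLT) that is not down to grade 2 within 5 days, does not respond to management, or occurs at 1 million IU. It then says: "In this case the patient will be removed from trial and the therapy will be deemed intolerable for that patient". Section 5.2 has: "If 1 million IU IL-2 is not tolerated the treatment will be deemed intolerable and patient removed from study". Section 5.2.2.3 gives the triggers as "If a DLT does not resolve within 5 days, is not responsive to management, or occurs at the lowest dose level" and ends in removal from the trial. Section 9.3 repeats the rule for a TLT: "then that patient will be removed from trial and the therapy will be deemed intolerable". Section 5.4.1.2 also describes the same patients, a little before the removal sentence, as leaving study treatment rather than the study.

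**Timing.** Note i to the calendar in section 6.1 places the second biopsy "during the final intralesional needle placement for IL-2 delivery (Cycle 2 Week 3"), which dates the last injection. Note g gives the scan schedule: "CT or MRI at pre-treatment and q 3 cycles until progression", with the end of cycle 3 as its first example. Section 8.1 instead puts the first response assessment at 6 weeks.

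**After early discontinuation.** The sections differ:
- Section 5.8: disease-status follow-up until progression for patients who stop for another reason.
- Section 7.2.5.4: imaging every 6 weeks, or per standard of care.
- Section 5.11: PFS and late toxicity every 3 months, within standard-of-care management.
- Section 6.1, note c: ORR, DCR and PFS every 3 cycles on treatment, but only PFS every 3 months after stopping early.

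**Analysis.** Section 7.1.4.3 says "All patients included in the study must be assessed for response to treatment", and "Patients in response categories 4-9 should be considered as failing to respond to treatment"; category 9 is unknown or not assessable. Section 5.9 calls a phase II patient evaluable only after at least 3 of the 4 injections.

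**The concern.** Abscopal response is the endpoint on which phase II is judged, in 21 patients. A site that applies the removal wording literally, or that works only from section 5.11 and note c, has no clear instruction to obtain the response scans in a patient removed for IL-2 intolerance. Such a patient would normally have no post-baseline scan yet. Section 7.1.4.3 requires a response assessment in everyone, so the plan asks for data that its own removal and follow-up wording may prevent from being collected. The plan also leaves two candidate rules for the denominator: section 7.1.4.3 keeps the patient as a failure, while section 5.9 may treat the patient as not evaluable.

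**Working it through.** **1. Does removal precede the first scan?** Inputs are 21-day cycles (section 5.2), IL-2 in weeks 2 and 3 of cycle 2 (calendar), a TLT period ending 7 days after the last injection and a 5-day resolution rule (section 5.4.1.2), and the first scan at the end of cycle 3 (note g). Visit windows are ignored.

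- Cycle 2 runs from day 22 to day 42, so its weeks 2 and 3 are days 29 to 42.
- Latest end of the TLT period: 42 + 7 = day 49.
- Latest end of the 5-day resolution rule: 49 + 5 = day 54.
- First scan: 3 × 21 = day 63, about week 9.

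Removal therefore comes at least about 9 days before the scan. Only under the 6-week time in section 8.1 (day 42) could a late event follow a scan.

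**2. When would the next assessment fall?** No text says when the follow-up clock starts. Assume it starts at removal, in weeks 5 to 7. Section 7.2.5.4 then gives weeks 11 to 13 (adding 6). Section 5.11 and note c give weeks 18 to 20 (adding 13). The calendar gives week 9. The standard-of-care allowances in 7.2.5.4 and 5.11 could narrow or remove this difference.

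**3. Reproduce the plan's power.** Section 9.1 gives n = 21, p0 = 0.05, p1 = 0.20, type I error 0.1 and power 0.82. With X ~ Bin(21, 0.20):

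P(X ≥ 3) = 1 − 0.8^21 − 21(0.2)(0.8^20) − 210(0.2²)(0.8^19) = 1 − 0.0092 − 0.0484 − 0.1211 = 0.821.

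This matches 0.82. The corresponding type I error is 0.085, within the nominal 0.1. Section 9.1 words the rule as more than 3 responders; that gives power 0.630 and type I error 0.019. This mismatch is a separate matter. The calculation below uses 3 or more because that reading reproduces the stated power.

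**4. Effect if section 7.1.4.3 governs.** Suppose m of the 21 are never scanned and count as failures, and the others respond independently at 20% (or at 5% for type I error). Power is P(Bin(21 − m, 0.20) ≥ 3), with type I error computed in the same way at 0.05.

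| m unscanned | Power, ≥3 | Type I error, ≥3 | Power, >3 as worded |
|---|---|---|---|
| 0 | 0.821 | 0.085 | 0.630 |
| 1 | 0.794 | 0.076 | 0.589 |
| 2 | 0.763 | 0.067 | 0.545 |

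The documents give no expected m. The nearest figure is 2 of 187 patients (1.1%) with grade 3 toxicity in section 4.8.4. It would imply 21 × 2/187 = 0.22 patients, but it counts a different event on other regimens, so it is only an indication that m may be small.

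**5. Effect if section 5.9 governs.** A patient removed after one or two injections has fewer than the 3 required and may leave the denominator. With two such patients dropped, 3 responders become 3/19 = 15.8% instead of 3/21 = 14.3%, and 4 become 4/19 = 21.1% instead of 4/21 = 19.0%. The reported rate then rises although no one else has responded. A patient removed after the third or fourth injection stays evaluable under either rule.

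**The case against.** The strongest reply is that the plan already handles this. Section 5.4.1.2 itself speaks of leaving study treatment, which suggests that removal means off treatment. Section 5.8 allows discontinuation at the investigator's decision and then follows disease status until progression. Section 7.2.5.4 provides imaging, and note g runs scans until progression rather than until the end of treatment. PFS needs images, and those images can also yield response. The standard-of-care phrases let the 6-week and 3-month schedules be reconciled. Section 5.7.3 uses similar removal wording for pregnancy and still requires follow-up.

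Much of this stands. A reader might infer that the plan forbids response assessment after removal. No text says so; the gap lies in what section 5.11 and note c leave out.

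The reply does not close the gap. Section 5.7.3 spells out its follow-up, and the IL-2 rules do not. The adverse-event reason in section 5.8 points to section 5.4.3, which covers pembrolizumab, not IL-2. Note g counts in cycles, and a removed patient may have no cycle 3. Note c names response on treatment and omits it after early discontinuation. Images taken for PFS at 3-month intervals could also be late for response. Section 5.2 refers to Figure 6, which I could not read; it may clarify the intended action.

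**Conclusion.** The point holds as a minor inconsistency. Removal normally precedes the first response scan, and the plan does not state plainly that scheduled response scans continue. If section 7.1.4.3 governs, the effect is a modest loss of power: about 0.03 for one unscanned patient and 0.06 for two. This assumes 3 or more responders as success, response unrelated to tolerance, and no scan at all in the removed patients.

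Two stronger readings are not supported. First, a reader might conclude that the effect is always conservative because unassessed patients are failures. That requires 7.1.4.3 to override 5.9, which the plan does not say. Second, a reader might take the 33% tolerability ceiling in section 9.3 as a likely removal rate; six of 21 unscanned would give power 0.602. The ceiling is a limit of acceptability, not an expectation, and sections 5.8 and 7.2.5.4 make it unlikely that every removed patient would go unscanned. Confidence is high on the timing and on the omission in 5.11 and note c, and lower on the size, since no intolerance rate is given for this combination.

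**What to change.** In sections 5.2, 5.2.2.3, 5.4.1.2 and 9.3, replace removal from the trial or study with wording such as:

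*IL-2 is permanently stopped and counted as treatment intolerance. Pembrolizumab is continued or stopped under sections 5.4.3 and 5.8. The patient stays on study, with response scans at the section 6.1 times counted from cycle 1 day 1 (the first at about week 9) until progression or new anticancer therapy, and with safety follow-up.*

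Counting from cycle 1 day 1 matters because the 6-week interval in section 7.2.5.4 does not by itself produce a week-9 scan. Add abscopal and overall response to the data listed in section 5.11 and note c after early discontinuation. State that these patients stay in the response denominator under section 7.1.4.3 whatever their injection count under section 5.9.

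The cost is wording in these places and possibly a few scans on the existing schedule.

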5.4.2 Hypofractionated Radiotherapy

Radiotherapy is delivered as a standard of care palliative regimen and radiotherapy related toxicities will be addressed using standard institutional practices. With a palliative dose of 24 Gy delivered in 3 fractions of 8 Gy each we anticipate minimal adverse effects for the treatment of dermal, subcutaneous, nodal, or liver lesions. The dose of radiotherapy can be reduced to no lower than 5 Gy per fraction at the discretion of the treating radiation oncologist in response to clinically significant treatment related toxicity at the treatment lesion or prior to the onset of treatment to respect normal tissue tolerances as deemed necessary by the treating radiation oncologist. If a dose of radiotherapy is missed it can be delayed. Any radiotherapy fractions not delivered during the week 1-2 of cycle 2 of therapy cannot be made up and those doses will be skipped.

5.4.3 Pembrolizumab

Adverse events (both non-serious and serious) associated with pembrolizumab exposure may represent an immunologic etiology. These adverse events may occur shortly after the first dose or several months after the last dose of treatment. See Section 5.6 for supportive care guidelines, including use of corticosteroids.

Table 9. Dose Modification Guidelines for Drug-Related Adverse Events

General instructions:

1. Corticosteroid taper should be initiated upon AE improving to Grade 1 or less and continue to taper over at least 4 weeks.
2. For situations where pembrolizumab has been withheld, pembrolizumab can be resumed after AE has been reduced to Grade 1 or 0 and corticosteroid has been tapered. Pembrolizumab should be permanently discontinued if AE does not resolve within 12 weeks of last dose or corticosteroids cannot be reduced to ≤ 10 mg prednisone or equivalent per day within 12 weeks.
3. For severe and life-threatening irAEs, IV corticosteroid should be initiated first followed by oral steroid. Other immunosuppressive treatment should be initiated if irAEs cannot be controlled by corticosteroids.

Immune-related AEs	Toxicity grade or conditions (CTCAEv4.0)	Action taken to pembrolizumab	irAE management with corticosteroid and/or other therapies	Monitor and follow-up
Pneumonitis	Grade 2	Withhold	
• Administer corticosteroids (initial dose of 1-2 mg/kg prednisone or equivalent) followed by taper	
• Monitor participants for signs and symptoms of pneumonitis• Evaluate participants with suspected pneumonitis with radiographic imaging and initiate corticosteroid treatment• Add prophylactic antibiotics for opportunistic infections
	Grade 3 or 4, or recurrent Grade 2	Permanently discontinue		
Diarrhea / Colitis	Grade 2 or 3	Withhold	
• Administer corticosteroids (initial dose of 1-2 mg/kg prednisone or equivalent) followed by taper	
• Monitor participants for signs and symptoms of enterocolitis (ie, diarrhea, abdominal pain, blood or mucus in stool with or without fever) and of bowel perforation (ie, peritoneal signs and ileus).• Participants with \geq Grade 2 diarrhea suspecting colitis should consider GI consultation and performing endoscopy to rule out colitis.• Participants with diarrhea/colitis should be advised to drink liberal quantities of clear fluids. If
	Grade 4	Permanently discontinue		

Immune-related AEs	Toxicity grade or conditions (CTCAEv4.0)	Action taken to pembrolizumab	irAE management with corticosteroid and/or other therapies	Monitor and follow-up
				sufficient oral fluid intake is not feasible, fluid and electrolytes should be substituted via IV infusion.
AST / ALT elevation or Increased bilirubin	Grade 2	Withhold	
 Administer corticosteroids (initial dose of 0.5- 1 mg/kg prednisone or equivalent) followed by taper 	
 Monitor with liver function tests (consider weekly or more frequently until liver enzyme value returned to baseline or is stable)
	Grade 3 or 4	Permanently discontinue	
 Administer corticosteroids (initial dose of 1-2 mg/kg prednisone or equivalent) followed by taper 	
Type 1 diabetes mellitus (T1DM) or Hyperglycemia	Newly onset T1DM or Grade 3 or 4 hyperglycemia associated with evidence of β -cell failure	Withhold	
 Initiate insulin replacement therapy for participants with T1DM Administer anti-hyperglycemic in participants with hyperglycemia 	
 Monitor participants for hyperglycemia or other signs and symptoms of diabetes.
Hypophysitis	Grade 2	Withhold	
 Administer corticosteroids and initiate hormonal replacements as clinically indicated. 	
 Monitor for signs and symptoms of hypophysitis (including hypopituitarism and adrenal insufficiency)
	Grade 3 or 4	Withhold or permanently discontinue ¹		
Hyperthyroidism	Grade 2	Continue	
 Treat with non-selective beta-blockers (eg, propranolol) or thionamides as appropriate 	
 Monitor for signs and symptoms of thyroid disorders.
	Grade 3 or 4	Withhold or permanently discontinue ¹		
Hypothyroidism	Grade 2-4	Continue	
 Initiate thyroid replacement hormones (eg, levothyroxine or liothyroinine) per standard of care 	
 Monitor for signs and symptoms of thyroid disorders.
Nephritis and Renal dysfunction	Grade 2	Withhold	
 Administer corticosteroids (prednisone 1-2 mg/kg or equivalent) followed by taper. 	
 Monitor changes of renal function
	Grade 3 or 4	Permanently discontinue		

Immune-related AEs	Toxicity grade or conditions (CTCAEv4.0)	Action taken to pembrolizumab	irAE management with corticosteroid and/or other therapies	Monitor and follow-up
Myocarditis	Grade 1 or 2	Withhold	
 Based on severity of AE administer corticosteroids 	
 Ensure adequate evaluation to confirm etiology and/or exclude other causes
	Grade 3 or 4	Permanently discontinue		
All other immune-related AEs	Intolerable/persistent Grade 2	Withhold	
 Based on type and severity of AE administer corticosteroids 	
 Ensure adequate evaluation to confirm etiology and/or exclude other causes
	Grade 3	Withhold or discontinue based on the type of event. Events that require discontinuation include and not limited to: Gullain-Barre Syndrome, encephalitis		
	Grade 4 or recurrent Grade 3	Permanently discontinue		

NOTE: For participants with Grade 3 or 4 immune-related endocrinopathy where withhold of pembrolizumab is required, pembrolizumab may be resumed when AE resolves to \leq Grade 2 and is controlled with hormonal replacement therapy or achieved metabolic control (in case of T1DM).
				

Dosing interruptions are permitted in the case of medical / surgical events or logistical reasons not related to study therapy (e.g., elective surgery, unrelated medical events, patient vacation, and/or holidays). Subjects should be placed back on study therapy within 3 weeks of the scheduled interruption, unless otherwise discussed with the Sponsor. The reason for interruption should be documented in the patient's study record.

